Robert Wood Johnson
Medical School

Department of Anesthesiology and
Perioperative Medicine
Rutgers, The State University of New Jersey
[name]
[name]

<http://rwjanesthesiology.rwjms.rutgers.edu>
p. [contact]
f. [contact]

August 3, 2022

Official Title:

Reducing Nausea and Vomiting During Cesarean Section with Regional Anesthesia: Is the Application of Scopolamine Patch with or without Intra-operative Acupressure Point P6 Stimulation more effective than Intra-operative Acupressure Point P6 Stimulation alone?

Document:

Study Protocol

NCT02960113

Title of Project:

**Reducing Nausea and Vomiting During Cesarean Section
with Regional Anesthesia: Is the Application of
Scopolamine Patch with or without Intra-operative
Acupressure Point P6 Stimulation more effective than
Intra-operative Acupressure Point P6 Stimulation alone?**

Principal Investigator:

[name]

Funding Source(s):

Rutgers Robert Wood Johnson Medical School

1. Purpose/Specific Aims

1. The purpose of this study is to compare the effectiveness of reducing intra-cesarean section nausea and vomiting with regional anesthesia in subjects who will receive scopolamine patch with acupressure point P6 stimulation versus subjects that receive just scopolamine patch versus subjects that receive just acupressure point P6 stimulation.

1.1 Objectives

The objective is to randomize subjects who undergo cesarean section with regional anesthesia into one of three groups to compare the efficacy of the therapies. Subjects will receive either (1) scopolamine patch or (2) acupressure point P6 stimulation or (3) scopolamine patch and acupressure point P6 stimulation to reduce intra-cesarean section nausea and vomiting.

1.2 Hypothesis

We suspect that there will be a difference in outcomes when comparing the three methods research arms and that one or more research arms will have a significantly lower mean rate of nausea and vomiting during cesarean delivery.

2. Background and Significance

Cesarean section is a procedure utilized by obstetricians in which an infant is delivered through a surgical incision in the mother's abdomen and uterus. This procedure requires adequate anesthesia usually obtained through one of three modalities: general, spinal, and/or epidural anesthesia. With general anesthesia, the patient is completely unconscious with the utilized agents affecting the entire body. Anesthesia-related maternal complications and mortality are lower when general anesthesia is avoided[1]. Regional anesthesia is the preferred option of healthcare providers when comparing the risks and benefits to the mother and her fetus[2].

Regional anesthesia, including spinal and epidural anesthesia, usually involves injecting varying concentrations and combinations of bupivacaine, ropivacaine, and fentanyl into the

Reducing Nausea and Vomiting During Cesarean Section with Regional Anesthesia: Is the Application of Scopolamine Patch with or without Intra-operative Acupressure Point P6 Stimulation more effective than Intra-operative Acupressure Point P6 Stimulation alone?

By **[name]**

subarachnoid or epidural spaces respectively [3, 4]. With epidural anesthesia, the mother is awake for the procedure and does not feel pain in the anesthetized area. Utilized anesthetic agents are continuously injected into the epidural space around the spinal cord that is usually occupied by fat. With spinal anesthesia, the mother is also awake but utilized agents are directly injected into the cerebral spinal fluid in lower doses than would be normally utilized with epidural anesthesia[5]. The advantages of these methods are effective pain relief without appreciable motor blockade, reduced risk of complications normally seen with general anesthesia, increased infantile APGAR scores at one and five minutes, and earlier bonding of mother with infant. Disadvantages include the inability to perform in mothers with coagulopathies or skin infections overlying the spine, increased reports of pain, and increased nausea and vomiting[4].

Nausea and vomiting are very common and unpleasant events experienced during cesarean section under regional anesthesia and in the postoperative period following cesarean section. These side effects are distressing for both the parturient and her family. In addition, intraoperative vomiting causes significant challenges for the surgeon[6], such as increased procedure length, increased risk of bleeding, increased risk of gastric content aspiration[7], and potential surgical trauma.

To combat the nausea and vomiting seen in all above anesthetic modalities, but to a greater degree in regional anesthesia, a number of pharmacological interventions are currently used with varying degrees of effectiveness in the perioperative period. These medications come from a wide range of drug classes including serotonin and dopamine receptor antagonists, corticosteroids, antihistamines, sedatives and anticholinergics[8].

The anticholinergics, namely scopolamine, have been shown to be effective at preventing nausea and vomiting if given before surgery. The mechanism of action is by antagonizing muscarinic cholinergic type 2 receptors, which are largely concentrated in the chemoreceptor trigger zone, nuclei tractus solitarii, and vestibular system[9]. This drug can be given orally, transdermally, subcutaneously, intramuscularly (IM), or intravenously (IV). In our hospital, we use this medicine for prophylactic antiemetic purposes through the transdermal delivery system (TDS), in the form of a patch. Common side effects reported with scopolamine therapy are dry mouth, blurred vision, drowsiness, dizziness, and mydriasis. Rare but serious side effects include disorientation, memory disturbances, dizziness, restlessness, giddiness, hallucinations, delirium, and confusion[10]. The drug can also readily cross the placenta, so it is administered to pregnant women only under observation. It is considered nonteratogenic and is compatible with nursing[11].

As evidenced above, the drugs currently used to prevent intra- and post-cesarean section nausea and vomiting are not without side effects. Other less expensive and safer alternatives have also been used with varying degrees of effectiveness in the treatment of perioperative nausea and vomiting. One non-pharmacological agent, P6 acupressure point stimulation, has been shown to be effective in reduction of post-operative nausea and vomiting. Based on the meta-analysis of 40 trials, involving 4858 patients, it was concluded that there is no differences in risks of postoperative nausea or vomiting after P6 acupressure point

Reducing Nausea and Vomiting During Cesarean Section with Regional Anesthesia: Is the Application of Scopolamine Patch with or without Intra-operative Acupressure Point P6 Stimulation more effective than Intra-operative Acupressure Point P6 Stimulation alone?

By **[name]**

stimulation compared to after administration of antiemetic drugs[12]. Additionally, the application of the acupressure point P6 stimulator has no known risks except for potential mild discomfort of the arm. However, only a few studies have been performed to determine if acupressure point P6 stimulation is effective in reducing intracesarean section nausea and vomiting under regional anesthesia, and the results are inconclusive[13].

In our study, we would like to compare the effectiveness of antiemetic agents or technique which cause less severe adverse reactions to the mother and her fetus. Out of the available pharmacological agents for reduction of intra-cesarean section nausea and vomiting, transdermal scopolamine patch is one of the safest medications. We would like to compare the effectiveness of the transdermal scopolamine patch with acupressure point P6 stimulation versus just transdermal scopolamine patch versus just acupressure point P6 stimulation.

3. Research Design and Methods

The design of the study consists of the randomization of subjects undergoing cesarean section with regional anesthesia in one of three groups. The study is not blinded; as the participants will know which method they are being treated with because of the difference in site and nature of the scopolamine patch and acupressure point P6 stimulation. The randomization of patients will be done by a computer to avoid bias before the informed consent form is signed by the patients. The computer will generate three sets of random numbers for the three groups. Once the consent form is signed, the investigator will allocate the patients serially to the groups having those numbers. The randomization will be created before the study begins and will assign 240 subjects into one of the three groups to receive the treatment as follows:

Group I (n=80): Will receive scopolamine patch placement on the skin behind the right ear 1 hour before initiation of the regional anesthesia for the duration of surgery. The time of the application of the patch will be recorded, and the time of the start of the surgery will be recorded. The last time point for evaluation of patient's nausea/vomiting will be when the patient arrives to the post anesthesia care unit. A member of the research team will remove the patch from the patient and properly dispose the patch upon arrival to the post anesthesia care unit.

Group II (n=80): Will receive acupressure point P6 stimulation. This is a stimulation of the chi channel at the master of the heart (MH8 position) at the small depression of the volar surface of the distal right forearm just above the crest of the wrist. The device will be put on the patients in the operating room prior to administration of the regional anesthesia and will be removed after the cesarean section is complete. The device will be removed from the patient in the operating room, before the patient is transported to the recovery room. Patients will receive continuous stimulation at a level that is comfortable for her prior to administration of the standardized regional anesthesia.

Reducing Nausea and Vomiting During Cesarean Section with Regional Anesthesia: Is the Application of Scopolamine Patch with or without Intra-operative Acupressure Point P6 Stimulation more effective than Intra-operative Acupressure Point P6 Stimulation alone?

By **[name]**

Group III (n=80): Will receive both scopolamine patch and acupressure point P6 stimulation, as described above.

The acupressure point P6 stimulation device is FDA approved for monitoring the magnitude of neuromuscular blocks in general anesthesia. This device stimulates the P6 acupressure point, which as demonstrated in previously published studies, is a safe acupressure point to be stimulated in pregnant women[14, 15]. However, to our knowledge, there are no published studies that have compared the effectiveness of this device versus the scopolamine patch versus the combination of the scopolamine patch and this device in preventing nausea and vomiting in women undergoing cesarean section under regional anesthesia. In this study, we would like to compare these three methods. The device will be used off-label in our study.

As per the RWJUH Obstetric Anesthesia Guidelines (Page 11, Section III B), metoclopramide, ondansetron, scopolamine patch, and acupressure point P6 stimulation may be applied prophylactically or therapeutically for the commonly complaints of nausea and vomiting.

Today, there are five types of procedures that are considered standard of care for obstetric patients undergoing cesarean section with regional anesthesia at the RWJUH. Each doctor gets to choose what he or she wants to do because for now, it is unclear which method is the best. (1) It is acceptable to not give any prophylactic nausea/vomiting therapy at the start of the anesthesia, (2) administer prophylactic metoclopramide and odansetron before beginning the anesthesia, (3) administer scopolamine patch prophylactically before beginning the procedure, (4) stimulate the P6 acupressure point before the start of the anesthesia and continue stimulating it throughout the procedure, or (5) administer scopolamine patch along with acupuncture point P6.

After the subjects have been randomly assigned to one of the three groups, subjects will receive the standardized regional anesthesia consisting of either spinal anesthesia with 10 milligrams of bupivacaine, 20 micrograms of fentanyl and 100 micrograms of epinephrine or epidural anesthesia with 20 milliliters lidocaine 2% along with 20 micrograms fentanyl and 100 micrograms epinephrine. Patients will offer their subjective assessments of the level of nausea on a scale of 0-10 (0 = no nausea, 10 = worst nausea every experienced) (See Appendix II) and objective assessments of whether or not the patients have vomited (See Appendix I) during 4 distinct points during the procedure. The 4 distinct points are as followed: after the administration of the regional anesthesia medications, after eversion of the uterus, after replacement of the uterus, and upon arrival in the post-operative recovery room. An Apfel score, which is used to predict the risk of experiencing post-operative nausea and vomiting, will also be determined with each subject (See Appendix I).

Other data that will be collected throughout the procedure and used for analysis and comparison (See Appendix I) include:

- Age, height and body weight
- ASA classification

Reducing Nausea and Vomiting During Cesarean Section with Regional Anesthesia: Is the Application of Scopolamine Patch with or without Intra-operative Acupressure Point P6 Stimulation more effective than Intra-operative Acupressure Point P6 Stimulation alone?

By [name]

- Gestational age
- Did patient have operative blood loss greater than 700cc? (yes or no); amount of blood loss
- If patient was hypertensive (systolic blood pressure above 140); what was the patient's highest blood pressure during the operation?
- If patient was hypotensive (systolic blood pressure below 90); what was the patient's lowest blood pressure during the operation?
- Hypoxia: Did intra-operative pulse oximetry drop <85%? (yes or no); what was the lowest pulse oximetry level of the patient during the operation?
- Efficacy of sensory block for cesarean section
- Nausea and vomiting treatment satisfaction
- Overall satisfaction

Study ID will be used for patient identification.

Of note, if at any point during the operation patients in any group report experience nausea and/or vomiting, they will be given a rescue dose of 4-8 milligrams odansetron with or without 10 milligrams metoclopramide and will be analyzed in their original group based on the statistical principle of intention to treat.

Copies of the subject assessments can be found in Appendix I and II.

3.1. Duration of Study

The study will be conducted for the duration of surgery until the parturient arrives at the post anesthesia care unit.

3.3 Sample Size Justification

This is a randomized unblinded prospective study comparing three different research arms in parallel. There will be three groups each having 80 subjects enrolled for the study. Sample size was determined using online software (Sealed Envelope, binary outcome superiority trial) to obtain power of 90%, two-tailed test at 5% significance level to detect 90% success rate in the combination arm (Scopolamine + acupressure) compared to either of other two arms (70% success rate).

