4.2 Dependent Variables or Outcome Measures

The study instrument that we will use is an assessment flowsheet to document:

1. ASA class
2. Age
3. Height

Reducing Nausea and Vomiting During Cesarean Section with Regional Anesthesia: Is the Application of Scopolamine Patch with or without Intra-operative Acupressure Point P6 Stimulation more effective than Intra-operative Acupressure Point P6 Stimulation alone?

By [name]

4. Gestational Age
5. Apfel Score (1-4)
6. Hypertension (systolic blood pressure greater than 140) (yes or no)
7. Highest Blood Pressure
8. Hypotension (Did blood pressure drop below 90 systolic at any point) (yes or no)
9. Hypoxia (Did intra-operative pulse oximetry drop <85 %?) (yes or no)
10. Lowest Pulse Oximetry (%)
11. Has Patient Vomited During Procedure (yes or no)
12. Did Patient Vomit After Administration of regional anesthesia (yes or no)
13. Did Patient Vomit After Eversion of Uterus (yes or no)
14. Did Patient Vomit After Replacement of Uterus (yes or no)
15. Did Patient Vomit Upon Arrival to Post-Operative Recovery Room (yes or no)
16. Has Patient Had Nausea During Procedure (yes or no)
17. Ranked Nausea After Administration of regional anesthesia (0-10, 0 = no nausea, 10 = worst nausea ever experienced)
18. Ranked Nausea After Eversion of Uterus (0-10, 0 = no nausea, 10 = worst nausea ever experienced)
19. Ranked Nausea After Replacement of Uterus (0-10, 0 = no nausea, 10 = worst nausea ever experienced)
20. Ranked Nausea Upon Arrival to Post-Operative Recovery Room (0-10, 0 = no nausea, 10 = worst nausea ever experienced)
21. Did Patient Have >700cc Blood Loss (yes or no), amount of blood loss _____
22. Efficacy of Sensory Block for Cesarean Section (1 = No Complaints, 2 = + Complaints, 3 = + Sedation N₂O or IV, 4 = G/A)
23. Nausea and Vomiting Treatment Satisfaction (0 = Not Satisfied, 10 = Extremely Satisfied)
24. Overall Satisfaction (0 = Not Satisfied, 10 = Extremely Satisfied)

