5.3 Subject Costs and Compensation

The subject will not incur additional costs outside of standard of care costs for medication that may be performed for routine standard of care. There will be no compensation for participation in this study.

6. Data Handling

All data will be stored in a locked file in the office of the principal investigator with limited access. The link to the protected health information will be stored separately from the study files and will be destroyed after all the data has been collected and analyzed. Up to 400 subjects may sign the informed consent for participating in this trial. This number is to ensure that 80 subjects complete each study group below. Therefore, we will be replacing subjects that do not complete the study as designed.

7. Statistical Analysis

There will be 3 treatment groups each having 80 subjects enrolled for the study. The intergroup analysis for numerical variables will be performed by ANOVA. All categorical variables will be analyzed with Chi-square/Fisher test. Descriptive statistics will provide the quantitative summaries for numerical data in each group.

The difference in end surgical nausea and vomiting will be analyzed using the Mann-Whitney rank sum test. Power analysis determined that 80 patients will be necessary in each group to detect the difference in treatment in nausea and vomiting, assuming a two sided alpha of 0.05 and power of 90%.

8. Data and Safety Monitoring

There is no data and safety monitoring committee for this study. Patients will be followed for adverse effects during their participation in this study. We will use Form FDA 3500A mandatory and Form FDA 3500 voluntary reporting forms found on the FDA website, www.fda.gov.

Reducing Nausea and Vomiting During Cesarean Section with Regional Anesthesia: Is the Application of Scopolamine Patch with or without Intra-operative Acupressure Point P6 Stimulation more effective than Intra-operative Acupressure Point P6 Stimulation alone?

By [name]

9. Reporting Results

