**Comments:**

The methods below are consistent with those mentioned in the protocol, after eliminating mention of unneeded procedures for looking at effectiveness of treatment. The methods also clarify the adjustment for multiple testing on the two primary outcomes.

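### The stated 90% power assumes one test at 0.05; with the SAP's doubled p-values it is about 87% (three-group test) or 84% (pairwise) per outcome, if the 70%/90% success rates apply to that outcome

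*Protocol*

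**What the plan says.** Protocol section 3.3 plans 80 subjects in each of three arms. The calculation is for a binary superiority outcome, "to obtain power of 90%, two-tailed test at 5% significance level to detect 90% success rate in the combination arm". The reference rate for that comparison is 70% in each single-treatment arm. Section 3.3 does not say what counts as success.

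Protocol section 4.2 has no success item. It lists two separate overall items: "Has Patient Vomited During Procedure (yes or no") and "Has Patient Had Nausea During Procedure (yes or no").

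Protocol section 7 says that "80 patients will be necessary in each group to detect the difference in treatment in nausea and vomiting". It attaches the same 0.05 level and 90% figure to that number. The sentence just before it names a different kind of test: "The difference in end surgical nausea and vomiting will be analyzed using the Mann-Whitney rank sum test".

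The SAP (Comments) calls its methods consistent with the protocol, "after eliminating mention of unneeded procedures for looking at effectiveness of treatment", and refers to two primary outcomes. Its Methods section tests yes/no nausea and yes/no vomiting over all time points by chi-square. Each of these two p-values is multiplied by 2. The Mann-Whitney test is not listed, and the SAP gives no power or sample size.

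**The concern.** Doubling a p-value and judging it at 0.05 is the same rule as testing the unadjusted p-value at 0.025. The protocol's power was calculated for a single test at 0.05. The SAP made the test of each outcome stricter without carrying the new level into the power statement, and because it describes itself as consistent with the protocol, a reader will carry the 90% forward.

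What is at stake is how a non-significant result on nausea or on vomiting is read. It would be weighed against a 90% power that the adjusted test does not have at the protocol's own rates. The undefined success adds to this, since the 70% and 90% cannot be tied to either primary outcome.

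**Working it through.** **Inputs.** 80 per arm; success 70%, 70%, 90%; two-sided 0.05; power 90% (Protocol 3.3 and 7). Two outcomes, chi-square, p-values doubled (SAP Methods). The SAP gives no threshold for the doubled p-value; I use the protocol's 0.05, the only level in the documents, so the level per outcome is 0.05 / 2 = 0.025.

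**Step 1: reproduce the plan's figure at 0.05.** With the unpooled two-proportion formula:

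n = (1.960 + 1.282)² × (0.7 × 0.3 + 0.9 × 0.1) / 0.20² = 10.51 × 0.30 / 0.04 = 78.8, so 79 per arm.

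At n = 80 the standardised difference is 0.20 / √(0.30 / 80) = 3.266, and power is Φ(3.266 − 1.960) = 90.4%. The stated 80 per arm and 90% are correct for one pairwise comparison at 0.05.

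**Step 2: the same formula at 0.025.** The critical value rises to 2.241, and power is Φ(3.266 − 2.241) = 84.7%.

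**Step 3: exact power of the uncorrected Pearson chi-square.** This sums binomial probabilities over all outcomes that reject (81³ = 531,441 count triples for the three-group test).

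| Test, n = 80 per arm | at 0.05 | at 0.025 |
|---|---|---|
| Three-group, 2 df, 70/70/90 | 92.3% | 86.8% |
| Pairwise, 1 df, 70 vs 90 | 90.3% | 84.4% |

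The shortfall against 90% is 3.2 points (three-group) or 5.6 points (pairwise). The exact size of the three-group test at a common rate of 70% is 0.0498 and 0.0249, so the nominal levels hold.

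Two points for anyone checking with other software. The noncentral chi-square approximation gives a lower three-group figure at 0.025, 81.7%. Fisher's test or a Yates correction lowers the pairwise figure at 0.025 to 79.7% or 78.7%.

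**Step 4: sensitivity to the assumed rates.**

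| Success rates | Three-group 0.05 → 0.025 | Pairwise 0.05 → 0.025 |
|---|---|---|
| 69/69/90 | 94.4% → 89.9% | 92.5% → 87.5% |
| 71/71/90 | 89.7% → 83.0% | 87.6% → 80.9% |
| 70/70/91 | 95.3% → 91.3% | 93.5% → 89.1% |
| 70/70/89 | 88.3% → 81.2% | 86.3% → 79.0% |

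The level of power moves with the inputs, but the step to 0.025 costs power in every row: 4.0 to 7.1 points three-group, 4.4 to 7.3 pairwise.

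**Step 5: if success meant freedom from both symptoms.** Failures are then 30%, 30% and 10%. Suppose a share s of failures includes the tested outcome, equal across arms (an assumption; the documents give no such share). The outcome-free rates become 1 − 0.3s, 1 − 0.3s and 1 − 0.1s.

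| s | Outcome-free rates | Three-group power at 0.025 |
|---|---|---|
| 100% | 70/70/90 | 86.8% |
| 90% | 73/73/91 | 80.8% |
| 75% | 77.5/77.5/92.5 | 68.9% |
| 50% | 85/85/95 | 41.6% |

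**Step 6: if 90% meant significance on at least one outcome.** Assume 70/70/90 holds for both outcomes. Simulation (200,000 trials per setting) with within-arm correlations of 0, 0.5, 0.7 and 0.9 gives 98.3%, 95.4%, 93.5% and 90.6% for the three-group test at 0.025.

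**The case against.** The strongest reply is that nothing in the protocol is miscalculated. It states its 0.05 openly, and for the test that the SAP most naturally describes the gap is only about 3 points. A one-point change in an assumed rate moves that power by more than this, and at 70/70/91 it exceeds 90%. The 84% belongs to a pairwise comparison that the SAP does not name. The 90% could also survive as the chance of significance on at least one outcome. Finally, section 6 of the protocol replaces non-completers. If replaced women stay in the intention-to-treat analysis, n per arm could exceed 80, and three-group power at 0.025 reaches 90% at 87 per arm.

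Much of this stands as qualification. The 80 per arm is correct at 0.05, the gap on the three-group test is modest, and the pairwise figure should be labelled as the sizing comparison. None of it makes the statement right as written. Input uncertainty applies equally at both levels, while the loss from 0.05 to 0.025 occurs at every input tried. Neither document defines 90% as power for at least one outcome. Both protocol power statements rest on 80 per group, so a larger analysed n is speculation.

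**Conclusion.** The point holds. The 90% figure applies to a single test at 0.05, which is not how the SAP tests either primary outcome. At the protocol's own rates, power per outcome is about 87% for the three-group chi-square and about 84% for the pairwise comparison used for sizing.

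This rests on three assumptions: the doubled p-value is judged at 0.05, 80 per arm are analysed, and 70/70/90% success applies to the outcome tested. The third cannot be checked from the documents. If success meant freedom from both symptoms, power per outcome is lower wherever some failures do not involve that outcome, by an amount the documents do not allow one to fix. The error concerns what is claimed about power; the validity of the tests is not in question.

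**What to change.** In Protocol sections 3.3 and 7, restate power at the level actually used, for example:

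> *With 80 per arm and success rates of 70%, 70% and 90% for [named outcome], power is 87% for the three-group chi-square [84% if the primary test is combination versus one single arm] at 0.025, the level per outcome after Bonferroni adjustment.*

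With it:

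- State in section 3.3 whether success meant no nausea, no vomiting, or freedom from both. If it meant both, say that the 90% applies to neither SAP primary outcome, and withdraw it or restate it with assumed rates for each outcome.
- If 90% was meant as the chance of significance on at least one outcome, say so and give the assumed correlation.
- State in section 7 that the power figure refers to the binary calculation in section 3.3 and not to the Mann-Whitney test.
- Add one SAP sentence saying whether the primary chi-square is three-group or pairwise.

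Date the change and mark it as a clarification. The test, the Bonferroni adjustment and the sample size stay as they are. The cost is wording only, with no extra patients; the one downside is a less favourable stated power.
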